7.2 Planned recruitment rate

We believe that approximately 30 European sites could participate. Therefore, we estimate that about 60-80 patients would need to be recruited per site to reach the total number of subjects required.

7.3 Statistical analysis plan

The statistical hypotheses are: 1) to show whether HIV infection is associated with severe COVID-19 compared to HIV uninfected individuals; 2) and to identify factors associated with severe COVID-19 within HIV infected population. All eligible subjects with a matching individual will be included in the analysis population (full population analysis).

Time-to-event methods, including Kaplan–Meier survival curves and Cox proportional-hazards models, will be used to compare PLWHIV with COVID-19 versus HIV seronegative COVID-19 controls for the severity of COVID-19 using parameters collected and adjusted for potential confounders. Conditional logistic regression models will be used to assess factors associated with COVID-19 within the group of PLWHIV to account for the case-control matching.

7.3.1 Summary of baseline data and flow of patients

All continuous variables will be summarised using the following descriptive statistics: n (non-missing sample size), mean, standard deviation (SD), 1st quartile, median, 3rd quartile, maximum and minimum. The frequency and percentages (based on the non-missing sample size) of observed levels will be reported for all categorical variables. The number of patients and the flowchart of the study will be presented.

7.3.2 Primary outcome analysis

The first primary outcome analysis will be performed on PLWHIV with COVID-19 versus HIV uninfected individuals with COVID-19. The endpoint is the occurrence of critical care admission (high dependency unit or intensive care unit), mortality in hospital or palliative discharge when discharged from hospital, or mortality at 6 weeks after diagnosis of COVID-19 or at discharge from hospital (where applicable). Kaplan-Meier estimates will be used to estimate the proportion of participants with the primary endpoint events. Unadjusted and adjusted hazard ratios (HR) will be estimated using the Cox proportional hazard model to assess the impact of HIV-infection on the severity of COVID-19. The validity of the proportionality assumption will be assessed and tested. The adjusted variables will be the following (potential confounders): Age (<60 vs 60-64 vs 65-69 vs 70-74 vs ≥75 years); Sex at birth (female vs male); Obesity (BMI>30 kg/m²); and Comorbidities (see appendix 1).

The second primary outcome analysis will be performed within the group of PLWHIV (PLWHIV with COVID-19 versus PLWHIV without COVID-19). The endpoint is to assess factors associated with severe COVID-19 within the group of PLWHIV. Conditional logistic regression models will be used to account for the case-control matching. The following variables will be assessed: Age (<60 vs 60-64 vs 65-69 vs 70-74 vs ≥75 years); Sex at birth (female vs male); Obesity (BMI >30 kg/m²); Comorbidities (see appendix 1); time since HIV diagnosis (years); current ART; CDC disease stage; CD4 cell nadir; last CD4 cell count/HIV-RNA before COVID-19 diagnosis (including CD4% and CD4/CD8 ratio) at baseline. For continuous variables, the decision to treat the variable as a continuous or categorical variable (as tertile) will be based on the lowest Akaike information criterion value for the corresponding univariable conditional logistic regression analysis. Variables achieving P < 0.20 in the univariable analysis will be retained for the multivariable analysis.

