4.1 Study Schema

[figure not shown]

Figure 1: Study design with cases (PLWHIV & COVID-19) and two matched control groups.

In total, 500 cases and up to 2500 controls will be analysed.

Only real-world retrospective data will be used for this study. Deidentified retrospective data will be transcribed into the eCRF system from source data at each clinical site or from existing COVID-19 cohort databases, where appropriate.

For comparing PLWHIV & COVID-19 versus HIV seronegative COVID-19 patients, a 1:1 and 1:3 matching will be performed according to the following criteria:

- Age (+/- 5 years)
- Sex
- Ethnicity (where available)
- Month of COVID-19 diagnosis (+/- 2 months)
- COVID-19 diagnosis inpatient, 1:1 matching
OR
- COVID-19 diagnosis outpatient (ambulatory), 1:3 matching

For comparing PLWHIV & COVID-19 versus PLWHIV without COVID-19, a 1:2 matching for similar risk of acquiring COVID-19 will be performed according to the following criteria:

- Age (+/- 5 years)
- Sex
- Ethnicity (where available)

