6 STUDY PROCEDURES

6.1 Subject Identification

Most PLWHIV will be identified from sites in the NEAT ID network. PLWHIV are routinely followed-up at specialised outpatient clinics with regular follow up visits as standard of care.

Since March 2020, more than 50 European sites have registered and started to provide basic information about the number of PLWHIV with COVID-19 and disease outcomes at their centres (<https://www.NEAT-ID.org/>). The dashboard provides a first estimate about the total numbers of PLWHIV with COVID-19 and where these patients are in continued care. As of 26th April 2021, 1,187 PLWHIV with COVID-19 were reported in care across Europe, with 436 hospitalisations and 78 deaths from an estimated number of 85,279 PLWHIV in routine care at these sites. These case numbers strongly suggest feasibility to recruit sufficient numbers of PLWHIV with COVID-19 and that patients have been identified at their centres already.

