6.2 Data collection

Only real-world retrospective data will be used for this study. Deidentified retrospective data will be transcribed into the eCRF system from source data at each clinical site or from existing COVID-19 cohort databases, where appropriate. No personal identifiable data will be transmitted to NEAT ID. The data elements will be transcribed from source data according to the data collection list below. Mechanisms to ensure data quality and integrity will be deployed as per applicable standard operating procedures and in line with GCP and GPP. Patients and controls will be identified and documented by participating sites, provided unbiased matching for inpatient/outpatient status at the time of COVID-19 diagnosis is ensured. Alternatively, and to avoid potential site-related bias during selection of HIV negative controls with COVID-19 diagnosed in hospital, data from matched controls will be obtained from appropriate existing COVID-19 cohort databases, e.g. LEOSS (Lean European Open Survey on SARS-CoV-2 infected patients) or ISARIC (International Severe Acute Respiratory and emerging Infection Consortium).

For all patients the following information will be collected:

- Age
- Sex
- Ethnicity (where available)
- Comorbidities (see appendix 1)
- Weight (kg) and height (m) (to calculate BMI)

For patients with COVID-19 the following information will be collected (where applicable):

- Date of positive PCR test result (documented or patient-reported)
- COVID-19 diagnosis inpatient or outpatient
- All-cause mortality in hospital, or palliative discharge, or mortality at 6 weeks after diagnosis of COVID-19 or at discharge from hospital
- Hospitalisation for COVID-19 and length of hospitalisation
- Critical care admission (high dependency unit or intensive care unit) for COVID-19 and length of stay in critical care
- Length of invasive ventilation
- Length of extracorporeal membrane oxygenation (ECMO)
- Need for kidney replacement therapy
- Inflammatory markers and blood cell counts at COVID-19 diagnosis¹ (if available):
 - Full blood cell count (Platelet count, RBC Count, WBC count (absolute), Haemoglobin, Haematocrit, MCV, MCH, Neutrophils, Lymphocytes, Monocytes, Eosinophils, and Basophils), ALT, AST, total bilirubin, urea, serum creatinine, calcium, glucose and HbA1C levels, total cholesterol, triglycerides, CRP, D-dimer, ferritin, and lactate dehydrogenase

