7 STATISTICS AND DATA ANALYSIS

7.1 Sample size calculation

The US Veterans Ageing Cohort Study (VACS) reported at AIDS 2020 [20] that the estimated proportion of non-HIV-infected individuals hospitalized with COVID-19 was 35%, 15% in ICU, 8% with invasive mechanical ventilation and 11% died. We anticipate a 1.1 to 2-fold increase in hazard rate in PLWHIV & COVID-19 (cases) relative to HIV-negative & COVID-19 (controls). With 500 cases and 1500 controls, a two-sided log-rank test at an alpha level of 0.05 will achieve at least 80% power to detect a 1.3-fold increase in the hazard rate of hospitalization, 1.4 for ICU, 1.6 for invasive mechanical ventilation and 1.5 for death (refer to Table 1 below). The power calculation was made using the statistical software package nQuery Advanced, with the two samples Log-Rank test module (Version 8.6.1.0).

Table 1

¹ Most recent available after positive SARS-CoV-2 PCR test, up to 10 days after positive test

		Cases (PLWHIV & COVID-19, N=500); Controls (HIV-negative & COVID-19, N=up to 1500) Alpha=5% (two-sided)										
Severity outcome	Outcome (%)	Power (%)										
Hazard Risk		1.1	1.2	1.3	1.4	1.5	1.6	1.7	1.8	1.9	2.0	
Hospitalization	35	20	60	90	99	>99	>99	>99	>99	>99	>99	
ICU	15	11	31	58	81	94	99	>99	>99	>99	>99	
Invasive mechanical ventilation	8	8	19	35	54	73	86	94	98	99	>99	
Death	11	9	24	46	68	85	95	98	>99	>99	>99	

For the search for factors associated with SARS-CoV-2 infection in PLWHIV, the recommended rule of thumb for sample size estimation for multivariable logistic regression models was $n = 100 + 50i$ where i refers to number of independent variables in the final model [34]. With 1500 PLWHIV (500 with COVID-19 and 1500 controls without COVID-19), we would be able to study 28 parameters with sufficient power to produce statistics that are nearly representative of the true values in the targeted population. However, sample size less than 1500 may be sufficient for associations that yield medium to large effect size.

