7.3.3 Secondary outcome analysis

All secondary outcome analysis will be performed on PLWHIV with COVID-19 compared to HIV uninfected individuals with COVID-19.

The proportion of hospitalised patients for COVID-19, the length of stay in hospital, the length of stay on ICU, the length of extracorporeal membrane oxygenation (ECMO), and the proportion of participants with a need for kidney replacement therapy will be estimated using the Kaplan-Meier estimate. Unadjusted and adjusted hazard ratios (HR) will be estimated using the Cox proportional hazard model to assess the impact of HIV-infection on the severity of COVID-19. The adjusted variables will be the same as those used for the first primary outcome analysis.

The number of ventilator-free days (VFDs) will be compared between groups using competing risk regression, with extubation and mortality a competing event, adjusted for potential confounders.

Linear regression models will be used to compare Charlson Comorbidity Index (CCI), the age-adjusted CCI (ACCI), 30-day mortality index after COVID infection, inflammatory marker and blood cell counts at COVID-19 diagnosis between the 2 groups, adjusted for potential confounders. The sample size will be quite large to consider CCI, 30-day mortality index, inflammatory marker and blood cell counts as normally distributed variables.

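### HIV-negative controls are matched 1:1 to inpatient and 1:3 to outpatient cases, but the primary Cox analysis ignores that status, which pushes the HIV hazard ratio above 1 even with no HIV effect

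*Combined protocol and SAP*

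**What the plan says.** Section 4.1 (and the synopsis) lets the number of HIV-negative controls depend on where the case was diagnosed: "COVID-19 diagnosis inpatient, 1:1 matching" or "COVID-19 diagnosis outpatient (ambulatory), 1:3 matching". Section 6.2 treats this status as important, since sites may supply controls only "provided unbiased matching for inpatient/outpatient status at the time of COVID-19 diagnosis is ensured", and it lists the status among the data to be collected.

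The first primary analysis (section 7.3.2) compares people with HIV and COVID-19 with HIV-negative COVID-19 patients by Kaplan-Meier and Cox methods: "Unadjusted and adjusted hazard ratios (HR) will be estimated using the Cox proportional hazard model to assess the impact of HIV-infection". The adjustment list that follows is explicit: age in five bands, sex, obesity and the Appendix 1 comorbidities. It names no stratum, matched-set term, weight or inpatient/outpatient covariate.

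Elsewhere the plan does provide for the matching. Section 7.3 assigns conditional logistic regression to the analysis "within the group of PLWHIV to account for the case-control matching", and section 7.3.2 repeats this for the second primary analysis. For the secondary Cox models, section 7.3.3 states: "The adjusted variables will be the same as those used for the first primary outcome analysis".

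**The concern.** A constant matching ratio leaves a matching factor equally distributed in cases and controls. A ratio that changes with the factor does not. Here outpatients are over-sampled among controls only, so the control group as a whole is diluted with patients diagnosed outside hospital. The primary endpoint is critical care admission, in-hospital death, palliative discharge or death at 6 weeks. It is plausible, though the documents do not state it, that patients already in hospital at diagnosis have the higher risk. In that case the pooled Kaplan-Meier curves separate and the hazard ratio rises above 1 purely through sampling.

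The error favours the hypothesis in section 3 that HIV worsens COVID-19 outcomes. A positive first primary result could therefore be partly or wholly produced by the matching ratio. The secondary Cox models inherit the problem, including the one for hospitalisation.

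**Working it through.** **The plan's own figures.** Section 7.1 claims at least 80% power for a "1.3-fold increase in the hazard rate of hospitalization, 1.4 for ICU, 1.6 for invasive mechanical ventilation and 1.5 for death" with 500 cases and 1,500 controls. Freedman's log-rank formula reproduces this. With φ = 500/1500, E = 500·p1 + 1500·p0 and p1 = 1 − (1 − p0)^HR, power is Φ(√(Eφ)·|HR − 1|/(1 + φ·HR) − 1.96). It gives 90.8%, 81.2%, 86.2% and 85.4%, against 90, 81, 86 and 85 in Table 1. The detectable range of 1.3 to 1.6 is thus a fair yardstick for the bias.

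**Inputs.**
- Ratios 1:1 and 1:3: section 4.1.
- Inpatient share of cases, f: not given. Section 6.1 reports "1,187 PLWHIV with COVID-19 were reported in care across Europe, with 436 hospitalisations and 78 deaths", so f = 436/1187 = 36.7% serves as a proxy. It counts anyone hospitalised, not only those diagnosed as inpatients, so it is probably an upper value. I also use 10% and 20%.
- Event risks by setting: not given; assumed over a range.

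**Step 1: imbalance created by the matching.** With k controls per outpatient case, the inpatient share of controls is f/(f + k(1 − f)), which is f/(3 − 2f) for k = 3. At f = 0.367, 500 cases give 500 × (3 − 0.735) ≈ 1,133 controls. Each group contains about 184 inpatients: 36.7% of cases, 16.2% of controls.

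**Step 2: hazard ratio with no HIV effect.** Each group's risk R is the mixture of inpatient and outpatient risks, and the null HR ≈ ln(1 − R_case)/ln(1 − R_control). For f = 0.367 and assumed risks of 40% and 3%:
- R_case = 0.367 × 0.40 + 0.633 × 0.03 = 0.166
- R_control = 0.162 × 0.40 + 0.838 × 0.03 = 0.090
- Null HR = ln(0.834)/ln(0.910) = 1.92

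| Assumed risk, inpatient/outpatient | f = 10%, k = 3 | f = 20%, k = 3 | f = 36.7%, k = 3 | f = 36.7%, k = 2 |
|---|---|---|---|---|
| 50%/2% | 1.86 | 2.10 | 2.12 | 1.60 |
| 40%/3% | 1.57 | 1.82 | 1.92 | 1.51 |
| 40%/5% | 1.38 | 1.60 | 1.74 | 1.43 |
| 30%/5% | 1.28 | 1.47 | 1.61 | 1.36 |
| 30%/10% | 1.13 | 1.23 | 1.34 | 1.22 |
| 20%/10% | 1.07 | 1.12 | 1.19 | 1.13 |

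The k = 2 column covers incomplete matching, with outpatient sets averaging two controls. For 50%/2% and k = 3 the maximum is 2.15, near f = 29%. Equal risks give 1.00. At f = 36.7% the implied overall risk among cases is 14% to 20%, close to the 15% ICU proportion used in section 7.1, so the grid is not extreme overall.

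**Step 3: does the planned adjustment remove it?** Cox models were simulated with no HIV effect, 2,000 replicates and one binary comorbidity. It was linked to inpatient status either weakly (prevalence 50% inpatient, 30% outpatient, HR 2) or strongly (70%, 20%, HR 3). Entries are adjusted HR, with rejection rate at nominal 5%.

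| f, risks, k | Weak link | Strong link |
|---|---|---|
| 36.7%, 40%/3%, k = 3 | 1.85 (98.5%) | 1.59 (88.8%) |
| 36.7%, 30%/5%, k = 3 | 1.55 (81.8%) | 1.36 (50.9%) |
| 20%, 30%/5%, k = 3 | 1.44 (53.9%) | 1.32 (33.8%) |
| 20%, 30%/10%, k = 3 | 1.21 (26.3%) | 1.13 (14.1%) |
| 36.7%, 40%/3%, k = 2 | 1.48 (75.0%) | 1.32 (44.9%) |

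A second simulation, at f = 36.7% with comorbidity, obesity and age all differing by setting, left adjusted HRs of 1.66 (40%/5%) and 1.34 (30%/10%).

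**Step 4: stratified analysis.** In the scenarios of Step 3, adding strata for inpatient/outpatient status gave HR 0.99 to 1.00 with 4.3% to 5.7% rejection. Stratifying by matched set gave HR 0.99 to 1.00 with 4.9% to 5.5% rejection (1,000 replicates).

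**The case against.** The plan is silent on strata; it does not say the data will be pooled. Section 7.3 speaks generally of adjusting for potential confounders, and status at diagnosis is collected, so an analyst might add it. This carries little weight: section 7.3.2 then gives a definite list without status, and handles matching only in the other primary analysis.

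The stronger objection concerns size, and it stands. Neither f nor the risks by setting are in the documents. The 36.7% figure is not inpatient status at diagnosis. Outpatients who are later admitted also have events, which narrows the risk contrast. In the mildest scenario shown with full 1:3 matching (20%/10%, f = 10%) the null HR is only 1.07, and a large observed hazard ratio could not then be blamed on sampling alone. The simulated covariates are also simpler than the planned age bands, sex, obesity and full comorbidity list, so the residual bias in the actual model is unknown.

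Finally, stratifying makes the HIV effect conditional on status at diagnosis, and any effect of HIV on being in hospital at diagnosis drops out. That is true, but matching on status has already removed that information.

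**Conclusion.** The concern holds. The direction follows from the design: if both kinds of case are enrolled and inpatients have the higher risk, the analysis as written gives a hazard ratio above 1 with no HIV effect. It is unbiased in this respect only if the risks are equal or only one setting occurs.

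The size is illustrative. Under full 1:3 matching the unadjusted null HR runs from 1.07 to 2.15 over the assumed inputs, and many scenarios fall in or above the 1.3 to 1.6 the study is powered to detect. In the simulations shown, adjusted null HRs were 1.13 to 1.85, with false-positive rates of 14% to 98.5%. Because this affects the first primary result, it must be corrected before analysis.

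**What to change.** In section 7.3.2, and by reference in 7.3.3, stratify the Cox models by matched set. This also carries diagnosis month and ethnicity, which are matched on but absent from the covariate list. If that loss of precision is unwelcome, stratify by inpatient/outpatient status at diagnosis, with variance robust to matched sets. Name one of these as primary, and state that the HIV effect is conditional on status at diagnosis.

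Present Kaplan-Meier curves and crude comparisons separately by status. Alternatively, weight each control by one over the number of controls actually matched in its set. For hospitalisation, a comparison within outpatient-diagnosed sets, labelled as subsequent admission, is a sensible option. It answers a narrower question than the present endpoint, and the main correction does not depend on it.

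The cost is SAP wording and a matched-set identifier in the dataset; status is already collected. In simulation, the standard error of the log hazard ratio rose by about 3% with status strata (0.148 to 0.152 at f = 36.7% and 40%/3%). With matched-set strata it rose by 8% to 12% (0.148 to 0.166, 0.155 to 0.170 and 0.178 to 0.192 in three scenarios).

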2. RATIONALE

Current evidence indicates that the risk of severe COVID-19 illness increases with age, male gender and with certain chronic medical problems such as arterial hypertension, cardiovascular disease, chronic lung disease, obesity and diabetes. Whether or not PLWHIV on treatment with a normal CD4 cell count and suppressed HIV-RNA are at an increased risk of serious illness or death, many will have other conditions that increase their risk. Indeed, almost half PLWH in Europe are older than 50 years and chronic medical conditions, including cardiovascular and chronic lung disease, are more common in PLWHIV.

Case series of PLWHIV with COVID-19 from China, Spain, Germany, Italy and the United States [10-22] show no clear evidence for a higher COVID-19 infection rate or different disease course in people with and without HIV. Of note, most case series of PLWHIV report a younger age in their study population than in HIV-negative hospitalised COVID-19 patients, but comparable rates of comorbidities. A cohort study from the United Kingdom reported a small potential increase in the risk of mortality among PLWHIV once hospitalised with COVID-19, albeit with no data around the risk of developing severe COVID-19 or hospitalisation among this cohort in the first place and no data on antiretroviral therapy (ART), viral load (VL) or CD4 count [23].

An analysis of risk factors for COVID-19 deaths in the Western Cape [24] described after adjusting for other risk factors that HIV increased a COVID-19 patient's death risk by a factor of 2.14 (95% CI 1.70;2.70), and active TB by a factor of 2.70 (95% CI 1.91-4.04). Finally, Spanish researchers described the incidence of COVID-19 and risk of hospitalization among 77,590 PLWHIV receiving ART [7]. During a 3-month period, 236 PLWHIV were diagnosed with COVID-19, and 151 were hospitalized. The risk of hospitalization by NRTI treatment per 10,000 persons was lowest for TDF/FTC (10.5), while other NRTI strategies were similar.

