3. OBJECTIVES AND OUTCOME MEASURES/ENDPOINTS

It is hypothesised that HIV infection is a risk factor for more severe COVID-19 outcomes and that advanced immunodeficiency as defined by current CD4 T-cell count or CD4 T-cell nadir is a risk factor for more severe COVID-19 outcomes in PLWHIV.

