- Drug treatment for COVID-19 (glucocorticoids, azithromycin, remdesivir, monoclonal antibodies against SARS-CoV2, convalescent plasma, anti-IL1 inhibitors, anti-IL6 inhibitors, lopinavir/ritonavir, and others)

For PLWHIV the following information will be collected:

- Date of HIV diagnosis
- Current ART
- CDC disease stage
- CD4 cell nadir
- Last CD4 cell count (including CD4% and CD4/CD8 ratio) and HIV-RNA before COVID-19 diagnosis, or most recent for HIV-only controls

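### Severity is compared with HIV-negative controls for PLWHIV as one group only, so an excess concentrated in a small low-CD4 group could be diluted and missed

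*Combined protocol and SAP*

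**What the plan says.** Section 3 states two hypotheses. One is that HIV infection is itself a risk factor for more severe COVID-19. The other is that, among PLWHIV, "advanced immunodeficiency as defined by current CD4 T-cell count or CD4 T-cell nadir is a risk factor for more severe COVID-19 outcomes".

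The first primary analysis in section 7.3.2 addresses the first hypothesis. It contrasts PLWHIV with HIV-uninfected individuals, all with COVID-19, and estimates unadjusted and adjusted HRs "to assess the impact of HIV-infection on the severity of COVID-19". The adjustment set is age band, sex, obesity and the Appendix 1 comorbidities. No CD4 or HIV-RNA level, stratum or interaction is planned. Section 7.3.3 uses the same two-group contrast for every secondary outcome.

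For PLWHIV, section 6.2 collects the CD4 nadir and "Last CD4 cell count (including CD4% and CD4/CD8 ratio) and HIV-RNA before COVID-19 diagnosis". These variables are analysed in the second primary analysis only. Its stated aim is factors for severe COVID-19 within PLWHIV, but it is specified as PLWHIV with COVID-19 against PLWHIV without it, and section 7.3 describes it as an analysis of factors associated with COVID-19.

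**The concern.** A single HIV term estimates an average over all PLWHIV in the sample. If the excess risk sits mainly in people with low CD4, and they are a small share of cases, the average lies close to that of the majority. The study could then report no association between HIV and severity while a minority carries a clear excess. Conversely, it could attach a modest average excess to everyone with HIV.

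The second primary analysis does not close the gap. It contains no HIV-negative patients, so it cannot place any CD4 group relative to people without HIV. PLWHIV without COVID-19 cannot have a severe COVID-19 outcome, so as specified the model concerns infection and not severity. The CD4 hypothesis is therefore not tested against severity in either primary analysis as written.

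**Working it through.** **Inputs from section 7.1.** The design basis is "With 500 cases and 1500 controls, a two-sided log-rank test at an alpha level of 0.05 will achieve at least 80% power". The control rates are given as "hospitalized with COVID-19 was 35%, 15% in ICU, 8% with invasive mechanical ventilation and 11% died". The HRs said to be detectable, beyond 1.3 for hospitalisation, are "1.4 for ICU, 1.6 for invasive mechanical ventilation and 1.5 for death". No rate is stated for the composite primary endpoint, so the 15% ICU rate stands in for it: 1,500 × 0.15 = 225 control events. The 1,500 controls are a maximum.

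**Assumed inputs (not in the documents).** s = share of cases with low CD4; h = HR in that group; HR 1 in other PLWHIV.

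**Step 1: reproduce Table 1, ICU row.** Freedman's log-rank formula is power = Φ(√(E·k)·|HR−1|/(1+k·HR) − 1.96), with k = 500/1500 and E the total number of events. At HR 1.4:
- case events = 500 × (1 − 0.85^1.4) = 101.7, so E = 326.7;
- √(326.7/3) × 0.4/1.467 − 1.96 = 0.89, so power is 81%, as in Table 1.

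Across HR 1.1 to 1.5 it gives 11, 31, 58, 81 and 94%, matching the row. The simpler events formula used below, SE² = 1/d₁ + 1/d₀ (events in the two groups), gives 80% at HR 1.4. Schoenfeld's formula gives 75%.

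**Step 2: dilution at s = 10%, h = 2.**
- Low-CD4 risk = 1 − 0.85² = 0.2775.
- Case risk = 0.9 × 0.15 + 0.1 × 0.2775 = 0.16275.
- Pooled HR = ln(1 − 0.16275)/ln(0.85) = 1.09.
- Case events = 500 × 0.16275 = 81.4. SE = √(1/81.4 + 1/225) = 0.129, z = 0.69, power 11%.

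**Step 3: the low-CD4 group against the same controls.**
- 50 cases × 0.2775 = 13.9 events.
- SE = √(1/13.9 + 1/225) = 0.277, z = 0.693/0.277 = 2.51, power 71%.
- An observed HR of 2 would have a 95% interval of 2 × exp(±1.96 × 0.277), about 1.2 to 3.4.

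**Step 4: range of shares at h = 2.** Schoenfeld: Φ(√(E·q(1−q))·ln h − 1.96), with q = n₁/(n₁ + 1500) and n₁ the low-CD4 cases.

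| Low-CD4 share (cases) | Pooled HR | Pooled power | Contrast: events formula | Contrast: Freedman | Contrast: Schoenfeld |
|---|---|---|---|---|---|
| 5% (25) | 1.05 | 6% | 44% | 48% | 27% |
| 10% (50) | 1.09 | 11% | 71% | 75% | 47% |
| 20% (100) | 1.19 | 28% | 93% | 95% | 76% |

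Simulated log-rank tests under the same assumptions (4,000 runs per setting) give 45, 66 and 89% for the contrast. With 1,000 controls they give 44, 66 and 88%.

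**Step 5: where the dilution stops mattering.** At s = 30% and h = 3, low-CD4 risk is 1 − 0.85³ = 0.3859 and case risk is 0.7 × 0.15 + 0.3 × 0.3859 = 0.2208. The pooled HR is then 1.53, with 96% power. For the pooled test to reach 80% power (Freedman), the low-CD4 share must be about 42% at h = 2 or about 23% at h = 3.

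**The case against.** **The pooled contrast is what the objectives ask for.** The two central questions in section 2, the objectives in 3.1 and the hypotheses in 7.3 all pair HIV against no HIV with factors within PLWHIV. Section 7.1 anticipates one overall HR of 1.1 to 2. This stands: the pooled HR validly answers the first hypothesis as an average.

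**Two stronger readings are not supported.** A reader might infer that section 3 expects the excess only in people with low CD4, so that a pooled HR near 1 is the predicted result. Section 3 does not confine the excess to low CD4, and it also hypothesises an effect of HIV itself. A reader might also take the section 2 clause "Whether or not PLWHIV on treatment with a normal CD4 cell count and suppressed HIV-RNA are at an increased risk" as a research question left unanswered. In its sentence it is concessive: it sets the matter aside and goes on to say that many PLWHIV have other conditions that raise their risk.

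**PLWHIV are not strictly one group in the adjusted model.** Appendix 1 lists AIDS among the comorbidities. If it is entered separately, the HIV coefficient describes PLWHIV without AIDS, and the dilution arithmetic fits the unadjusted HR best. This stands in part, but the item is undefined and is not the same as current CD4, so it does not supply the missing contrast.

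**CD4 belongs to the second primary analysis.** That is the evident intention, but the comparison specified there does not model severity.

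**The size follows from chosen inputs, and the added analysis may itself be underpowered.** Both are true. The share and h are assumptions, and the formulas disagree about the small group (47% to 75% at a 10% share). Splitting by CD4 improves the chance of seeing such an excess without guaranteeing it.

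**Conclusion.** The point holds as a gap that is cheap to close. No planned severity comparison with HIV-negative controls is graded by CD4, and as written CD4 is not tested against severity in either primary analysis. An excess concentrated in a low-CD4 group of 5-20% of cases at HR 2 would leave the pooled test with 6-28% power, against about 44-93% for a direct contrast (27-76% by Schoenfeld).

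These figures rest on an assumed share and effect, HR 1 in other PLWHIV, the ICU rate as a stand-in for the composite, and the maximum number of controls. They show that a null pooled HR could be misleading, not that one is expected. The pooled analysis is not invalid and should stay.

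**What to change.** In section 7.3.2, keep the pooled HR and add one pre-specified supplementary Cox model for the primary endpoint, with the same controls and covariates apart from AIDS:

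- **Exposure:** HIV-negative (reference); PLWHIV with last CD4 below a cut-off fixed in the plan before analysis; PLWHIV at or above it. Use HIV-RNA suppression as a separate sensitivity definition, so that the low-CD4 group is not a mixture.
- **AIDS:** leave it out of the covariates in this model, because it occurs only in PLWHIV and overlaps with the exposure.
- **Missing data:** exempt CD4 from the 15% exclusion rule in section 7.5, or report a complete-case version. Count missingness among PLWHIV only, since controls without HIV have no CD4 value to collect.
- **Reporting:** give both HRs with intervals, and state that a null pooled HR does not rule out an effect in the low-CD4 group.

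The cost is a few lines of plan text and one more model on variables section 6.2 already collects. The downside is one further test and a low-CD4 group of perhaps 25 to 100 cases under the assumed shares, with a correspondingly wide interval.
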